The intervention group attended BCC sessions on menstrual health, diet, and physical activity from May to June 2023, with bi-monthly follow-ups through January 2024. The control group did not receive any educational intervention. The dysmenorrhea outcome analysis included 234 participants from the intervention group and 238 from the control group. In the case of PMS and MI, 228 participants with complete and valid data were analyzed per group. To ensure baseline comparability, final analyses included 98 matched participants per group (n=196) after propensity score matching.

Total number affected by all-cause mortality

- Not applicable as the participants received the non-invasive nature of the behavioral intervention.

Total number at risk for all-cause mortality

- Not applicable as the participants received the non-invasive nature of the behavioral intervention.

Total number at risk for serious adverse events

- Not applicable as the participants received the non-invasive nature of the behavioral intervention.

Total number affected by any serious adverse event

- Not applicable as the participants received the non-invasive nature of the behavioral intervention.

Limitation and caveats

This quasi-experimental study lacked randomization, which may have introduced residual confounding and limited causal inference. About 4% of intervention participants missed sessions or follow-up, possibly underestimating the true effect. While the study aimed to reflect real-world settings by conducting sessions in academic institutions, potential confounding factors related to control group characteristics were not assessed. Dietary intake quantity was not measured, and 24-hour recalls may have been impacted by recall bias, affecting data accuracy.

Certain Agreements

Are all PIs employees of sponsor?

- Yes: The principal investigator (PI) is an employee of the sponsor

There were no agreements restricting the principal investigators from discussing, presenting or publishing the study results. The study was self-financed without external sponsorship.

Results point of contact

Name or official title: [name]. [name], principal investigator (PI) of the study

Organization name: Shahjalal University of Science and Technology, Sylhet, Bangladesh

[contact]

Email: [contact]

References

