A total of 498 participants (249 in each group) were initially enrolled, based on power calculations designed to detect a 30% reduction in the prevalence of menstrual disorders, with 80% statistical power and 95% confidence level. After exclusions for missing data and loss to follow-up, 234 intervention and 238 control participants were included in the analysis of dysmenorrhea; and 228 participants per group were retained for PMS and MI outcomes. To reduce selection bias and ensure covariate balance, 1:1 nearest-neighbor propensity score matching (PSM) was applied using a logistic regression model with a caliper of 0.01 and no replacement. The final matched sample included 196 participants (98 per group) for each outcome.

Among all the primary outcomes, dysmenorrhea was assessed using the Andersch and Milsom (4) four-point scale and dichotomized as no pain (Grade 0) vs. any pain (Grades 1 – 3). PMS was evaluated by the premenstrual symptoms screening tool (PSST) and recoded into a binary variable: No/Mild PMS (code = 0) and Moderate to Severe PMS or premenstrual dysphoric disorder (PMDD) (code = 1) (5). Additionally, Menstrual irregularity was determined based on self-reported cycle length and coded as irregular (1) if <21 or >35 days, and not irregular (0) if within the 21–35 day range (6).

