Completed	Dysmenorrhea	234 (Intervention), 238 (Control)	Participants included after cleaning for dysmenorrhea outcomes.	Valid responses	472
	PMS and MI	228 (Intervention), 228 (Control)	Final sample included participants with valid PMS and IMC outcome data	Appropriate responses	456
Not completed	Dysmenorrhea	8 (5 intervention and 3 control)	Omitted from the final dataset due to	Incomplete response	8

			data quality issues, including missing or invalid responses		
	PMS and MI	24 (11 intervention and 13 control)	Removed from analysis because of incomplete or inaccurate data.	Invalid response/missed data	24

Table 4A. Participation flow of matched sample for post-intervention dysmenorrhea analysis

Participation status	Groups	Data (number of participants)	Comments	Milestone title	Milestone data (number of participants)
Started	Intervention	234	Out of 234 eligible participants, 98 were selected using PSM and individually matched in a 1:1 ratio with control participants within the common support region.	Enrollment	472
	Control	238	All participants initially eligible; matched pool was drawn from this group		
Completed	Intervention	98	All 98 matched completed the post-intervention evaluation	Matching completion and final outcome analysis	196
	Control	98	98 matched controls completed the evaluation and the remaining controls not matched due to 1:1, no-replacement rule		
Not completed	Intervention	136	The participants were excluded from the analysis because they could not be matched with any control participants within the specified caliper of 0.01	Excluded due to fall outside the region of common support	276
	Control	140	Even though these participants fell within the common support region, they were excluded because of the 1:1 matching requirement and the no-replacement rule.		

Table 4B. Matched sample of participants for post-intervention assessment of PMS and MI outcomes

Participation status	Groups	Data (number of participants)	Comments	Milestone title	Milestone data (number of participants)
Started	Intervention	228	From the pool of 228 eligible participants, 98 were chosen using PSM and matched one-to-one with control participants within the common support region.	Enrollment	456
	Control	228	A subset of matched participants was selected from all 228 initially eligible control individuals		

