Completed	Intervention	98	All 98 participants in the matched group successfully completed the post-intervention assessment.	Matching completion and final outcome analysis	196
	Control	98	The evaluation was completed by 98 matched control participants while the rest were excluded in accordance with the 1:1 matching and no-replacement criteria.		
Not completed	Intervention	130	As no matches within the caliper of 0.01 could be identified, the participants were excluded from the analysis	Participants were excluded as they did not fall within the region of common support.	260
	Control	130	Despite being within the common support region, these participants were excluded to maintain the 1:1 matching ratio and adhere to the no-replacement rule.		

Baseline characteristics

Group information

Group title

1. Intervention Group
2. Control Group

Group description

The intervention group included participants who attended all three sessions of the BCC module on menstrual health management. Initially, 249 participants were recruited, and 242 completed all sessions. At the six-month follow-up, 239 participants completed the outcome assessment. After data cleaning, 234 participants were eligible for the final analysis of the dysmenorrhea outcome, while 228 participants had valid data and were included in the analyses of PMS and MI.

Participants in the control group did not receive the BCC intervention but were matched in number and characteristics to the intervention group. Initially, 249 participants were listed for the control arm, and 241 completed the outcome assessment interview. Following data quality verification, 238 participants were included in the final analysis for the dysmenorrhea outcome. For the PMS and MI outcomes, 228 participants had valid and complete data and were included in the respective analyses.

After propensity score matching, 98 matched participants from each group (n=196) were used for the final analysis of each outcome variable, ensuring balance between the groups on key covariates.

Baseline analysis population information

The baseline analysis populations differ slightly from the initial recruitment numbers due to participant withdrawal, non-response, absence during sessions or protocol violation, and exclusion based on data quality checks for outcome variables (Table 5).

Table 5. Baseline Profile of Participants by Study Group: Intervention vs. Control

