Participants in the control group did not receive the BCC intervention or any related educational sessions but were matched with the intervention group based on number and baseline characteristics. Of the 249 participants initially enrolled in the control arm, 241 completed the outcome assessment interview. After data quality checks, 238 participants were retained for the final dysmenorrhea analysis. For the PMS and MI outcomes, 228 participants with complete and valid data were included in their respective analyses.

After propensity score matching, 98 matched participants from each group (n=196) were used for the final analysis of each outcome variable, ensuring balance between the groups on key covariates.

Analysis population information

This section provides (Table 9) an overview of the analysis populations for each outcome measure, including the number of participants at baseline and after propensity score matching. It also outlines the methods used to define the final samples included in the analyses.

Table 9. Overview of analysis population by groups for outcome measures

Outcomes	Group	Overall number of participants analyzed	Analysis population description
Dysmenorrhea	Intervention	234	Following initial recruitment and data quality verification, 234 participants in the intervention group and 238 in the control group were eligible for analysis. However, Final analyses were conducted using 1:1 propensity score matching without replacement and a caliper of 0.01, yielding a matched sample of 196 participants (98 from each group).
	Control	238	
	Total	472	
PMS and MI	Intervention	228	For both PMS and IMC outcome measures, 228 participants from each group provided valid and complete responses for the baseline analysis. Following 1:1 propensity score matching without replacement (caliper = 0.01), 98 participants per group were retained, yielding a final matched sample of 196.
	Control	228	
	Total	456	

Outcome measure data

Table 10 represents the outcome measure data for all participants who completed the follow-up assessment. Results are shown separately for the intervention and control groups, with each outcome reported as the number and percentage of participants. The data reflect the prevalence of each specified condition at follow-up, according to group assignment.

Table 10. Prevalence of key menstrual disorders among participants in control and intervention groups

Outcome variables	Control (n = 238)	Intervention (n = 234)	Total (N = 472)

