
Statistical Analysis Plan (SAP)

Statistical analysis overview

Statistical analyses were conducted to evaluate the impact of the BCC intervention on three binary outcomes: dysmenorrhea, PMS, and IMC. Categorical variables were summarized as frequencies and percentages and analyzed using the chi-square (χ^2) test. Continuous variables were presented as means with standard deviations and compared using independent t-tests. To adjust for potential baseline imbalances between the intervention and control groups, propensity score matching (PSM) was carried out using logistic regression. A 1:1 nearest-neighbor matching algorithm was applied with a caliper width of 0.01 and without replacement. Post-matching covariate balance was assessed using standardized mean differences (with a bias threshold of <10%) and chi-square tests. The primary analysis of intervention effects was conducted using conditional logistic regression on the matched sample. To validate the findings, bivariate and multivariate logistic regression analyses were also performed on the unmatched dataset. Additionally, sensitivity analyses were conducted to ensure the robustness and consistency of the results, including covariate balance diagnostics, estimation of the average treatment effect (ATE) and the average treatment effect on the treated (ATT), and Bayesian logistic regression on the matched sample.

Comparison group selection

1. Intervention Group (received BCC module)
2. Control Group (did not receive BCC module)

Type of statistical test: Superiority

- Comments: The analyses were designed to assess whether the BCC intervention group had superior outcomes compared to the control group using fixed-effect models on matched pairs. Power calculations were based on expected reductions in outcome prevalence.

Statistical test of hypothesis

Conditional logistic regression was used to estimate the odds of binary outcomes between intervention and control groups after matching.

- P-Value: < 0.05
- Comments (P-Value): A p-value < 0.05 was considered statistically significant. No adjustments for multiple comparisons were made. Results were considered statistically significant at $p < 0.05$.

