- Method: Chi-squared, t-test, regression (logistic), conditional logistic regression
- Comments (Method): Pre- and post-PSM tests used Pearson's chi-square; conditional logistic regression applied to matched data; bivariate and multivariate logistic regression used for robustness checks

Method of Estimation

- Estimation Parameter: Odds Ratio (OR)
- Estimated Values: Reported as crude odds ratios (COR) and adjusted odds ratios (AOR). Coefficient value was used to estimate ATE and ATT (Table 11).
- Confidence Interval Level: 95%
- Number of Sides: 2-sided
- Lower and upper limit: Reported per outcome (see Table 11)

- Parameter Dispersion Type: Standard error of the mean
- Estimation Comments: Odds ratios compared the intervention group (numerator) to the control group (reference) for menstrual outcomes. Odds ratios reflect the likelihood of menstrual outcomes in the intervention group relative to the control group. ATE and ATT were also estimated using PSM.

Table 11. Estimated odds ratios from bivariate and multivariable (before matching) as well as conditional (after matching) and logistic regression models assessing the impact of the BCC module on menstrual health outcomes

Outcomes	Before matching		After matching
	COR (95% CI)	AOR (95% CI)	AOR (95% CI)
Dysmenorrhea	0.07 (0.04, 0.11)***	0.13 (0.06, 0.26)***	0.13 (0.05, 0.34)***
Premenstrual syndrome	0.07 (0.04, 0.11)***	0.13 (0.07, 0.23)***	0.12 (0.06, 0.27)***
Menstrual Irregularity	0.12 (0.07, 0.20)***	0.26 (0.14, 0.48)***	0.21 (0.09, 0.45)***

* Indicated chi square value define the level of significance i.e. * $p < 0.05$, ** $p < 0.01$, *** $p < 0.001$

Other statistical analysis

Additional scientifically appropriate analyses were conducted to ensure robustness and validity of the findings:

1. **Propensity Score Matching (PSM):** PSM was used to control for baseline differences between the intervention and control groups. Participants were matched 1:1 using nearest-neighbor matching with a caliper width of 0.01 and without replacement. Covariate balance was assessed using standardized mean differences (bias <10%) and post-matching chi-square tests.

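### The stated 80% power belongs to 249 enrolled per group; the primary analysis uses 98 matched pairs, where the same premise gives about 42%

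*Combined protocol and SAP*

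**What the plan says.** The protocol, under Detailed description of the study, gives the only numerical power statement. It says that 498 participants, 249 per group, were enrolled "based on power calculations designed to detect a 30% reduction in the prevalence of menstrual disorders, with 80% statistical power" and 95% confidence. The same paragraph then reports 234 and 238 analysable for dysmenorrhea, 228 per group for PMS and menstrual irregularity (MI), and finally: "The final matched sample included 196 participants (98 per group) for each outcome".

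The SAP, under Statistical analysis overview, says: "The primary analysis of intervention effects was conducted using conditional logistic regression on the matched sample". Under Type of statistical test it adds "Power calculations were based on expected reductions in outcome prevalence", with no number. Table 9 confirms for dysmenorrhea that "Final analyses were conducted using 1:1 propensity score matching without replacement and a caliper of 0.01, yielding a matched sample of 196 participants", and gives 98 per group for PMS and MI as well.

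Tables 4A and 4B account for the loss. For dysmenorrhea, 136 intervention participants "could not be matched with any control participants within the specified caliper of 0.01" and 140 controls were left over. For PMS and MI, 130 per group were left out; the reason given on the intervention side is "As no matches within the caliper of 0.01 could be identified".

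The documents do not state the control prevalence used in the power calculation, the outcome it was based on, whether 30% is relative or absolute, or any allowance for attrition or matching loss.

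**The concern.** The stated power and the primary analysis refer to different samples. Ordinary attrition and data cleaning took 249 per group to between 228 and 238. Matching then removed a further 130 to 140 per group. That second loss follows from the chosen analysis method, so the sample-size statement for this design needs to address it.

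At stake is how the planning claim is read. A reader who carries the 80% over to the primary comparison applies it to a sample 2.5 times smaller than the one it is attached to. Unless a large allowance was built into 249, the described design does not deliver the stated power for the analysis it names as primary.

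**Working it through.** **Inputs.** Enrolled 249 per group, 80% power and 95% confidence (Detailed description). Matched sample 98 per group (Detailed description; Tables 4A, 4B and 9). Two-sided 0.05: the SAP gives two-sided intervals and p<0.05; that the power calculation was also two-sided is an assumption.

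**1. Can 249 be reproduced?** Not from the documents, because the control prevalence and the meaning of 30% are missing. With the pooled two-proportion formula, two-sided, no allowance and a 30% relative reduction, 249 per group gives 80% power at a control prevalence of about 39.4% (39.4% against 27.6%). The documents do not give that prevalence. The background figure of up to 75% would need only 71 per group. A 30-point absolute reduction needs at most about 43 per group.

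**2. Ratio of samples.** 98/249 = 0.394; 249/98 = 2.54.

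**3. Power at 98, taking 249 as giving 80%.** Power is approximately Φ(δ − 1.96), where δ is the effect divided by its standard error and grows with √n.
- At 249: δ = 1.960 + 0.842 = 2.802.
- At 98: δ = 2.802 × √(98/249) = 2.802 × 0.627 = 1.758.
- Power = Φ(1.758 − 1.960) = Φ(−0.202) = 0.42.

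The control prevalence and the effect scale do not enter this step. As a check, the pooled formula was solved for the difference that gives 80% at 249, at control prevalences from 10% to 95%. Power at 98 was 41.8% each time.

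**4. If 249 contained an allowance a.** The 80% then belongs to 249 × (1 − a) per group, and power at 98 is Φ(2.802 × √(98/(249(1 − a))) − 1.960).

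| Allowance a | Size carrying the 80% | Power at 98 |
|---|---|---|
| 0 | 249.0 | 42% |
| 10% | 224.1 | 46% |
| 20% | 199.2 | 50% |
| 40% | 149.4 | 62% |
| 61% (1 − 98/249 = 0.606) | 98 | 80% |

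**5. Pair correlation.** Asymptotic McNemar power for 98 pairs, at 39.4% against 27.6%, is 41%, 45%, 49% and 54% at correlations of 0, 0.1, 0.2 and 0.3.

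**6. Sidedness.** If the calculation was one-sided at 0.05, the scaling in step 3 gives Φ((1.645 + 0.842) × 0.627 − 1.645) = 0.47.

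Covariate adjustment in the matched model is not included in any of these figures.

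**The case against.** The strongest reply is that the study is complete and none of its results is inconclusive. Table 11 gives matched odds ratios with upper 95% limits of 0.34, 0.27 and 0.45, all p<0.001. The intervals now carry the precision, and low planned power mainly threatens inconclusive findings. This stands, and it limits the point to the planning statement. Nor is anything hidden: the fall to 98 per group is reported several times, and no sentence claims 80% for the 98 pairs.

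A second reply is that 249 may have included an allowance for matching. The documents do not exclude it, so a flat statement that the 80% cannot apply to the matched analysis would go too far. But the allowance would have to be about 61%, and none of any size is described.

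A third is that 98 per group is ample if 30% means 30 percentage points: power is then at least 99% at any control prevalence. The arithmetic is right, but it does not rescue the stated figure. On that reading 249 per group would have far more than 80% power, unless at least 1 − 43/249 = 83% of it was allowance. The 42% takes the 80% at 249 as stated; if that premise fails, the 42% falls with it and the planning statement needs correcting for a different reason.

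Two stronger readings are tempting. A reader might infer that the study was underpowered for its actual effects or that its results are unreliable; neither follows. A reader might also compute per-outcome power from the observed control prevalences in Table 10. For a 30% relative reduction, those prevalences (87.8% dysmenorrhea, 63.6% PMS, 48.2% MI) give 91% to over 99% power at 249, so they do not fit the stated design. They are also post-intervention, unmatched data, and the MI count has to be rebuilt from a row that does not add up. They cannot stand in for the missing design inputs.

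**Conclusion.** The point holds as a mismatch between a stated power and the analysis it would be read as describing. With 249 per group taken as giving 80% at two-sided 0.05, with no allowance and no pair correlation, the matched primary comparison has about 42% power. A 20% allowance raises this to about 50%, and a pair correlation of 0.3 without an allowance to about 54%. Only an undocumented allowance of about 61% restores 80% in the absence of pair correlation; with positive correlation the required allowance is smaller. The true design power at 98 pairs cannot be fixed without the missing inputs. The reported effect estimates and p-values do not change.

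**What to change.** In the Detailed description, state that the 80% applies to the comparison of 249 enrolled per group and, unless an allowance for matching loss was built in, not to the matched primary analysis. If there was an allowance, state its size. Give the design inputs: control prevalence, the outcome used, relative or absolute reduction, and any attrition or matching allowance. From those inputs, restate the design power or the detectable reduction for 98 pairs, and refer to it where the SAP mentions power under Type of statistical test.

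If the inputs cannot be recovered, say so and report only the conditional figure: about 42% at 98 per group if 249 gives 80%, labelled as assuming no allowance and no pair correlation. Do not insert detectable reductions computed from the observed outcome prevalences.

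The cost is wording only, with no further enrolment and no reanalysis. Unless a large allowance is documented or the recovered inputs show otherwise, the planning statement becomes less favourable.
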